- **Assessment-only:** All assessments will be conducted, but no intervention will be provided to this group. The assessment only condition is necessary for investigating natural trajectory and form the baseline level for assessing risk reduction in the interventional groups.

Figure 1. Screenshot from GooglePlay of the “Tankevirus” smartphone app.

All interventions and assessments for all trial arms will be fully digitalized through a research app, which is essentially a modification to the already developed “Tankevirus”-app, including all preassessments and follow-ups. Human interaction is limited to the therapist-led group, otherwise automated nudges and notifications will remind the adolescents to complete assessments. This will be beneficial when considering the scalability and implementation of the intervention, should it be successful, and for evaluating whether human interaction indeed is a driver of the effect between interventions.

HYPOTHESIS: The main hypothesis is that the outcome related to the therapist-guided group intervention will be more effective in reducing number of relapses and time to relapse during the follow-up period when compared to the app-based approach, and that the app-based approach will be more efficacious compared to an assessment-only condition/care-as-usual (the control group).

PARTICIPANTS: Participants will primarily be recruited through large scale marketing campaign in social media (i.e., TikTok, Snapchat, Instagram) and web pages of user organizations, informing about this trial and the opportunity to take part. This is the most efficient way of reaching eligible participants, as clinicians seldom refer to such a trial ([name], PI of the StayFine-trial targeting adolescents in remission, *personal communication*, 21.07.24). Overall, 90 % of Norwegian adolescents are on social media (30). Currently, we have established contact with the social media coordinator in Mental Helse Ungdom. We will also post physical adds at places we expect adolescents to see them. Through other ongoing projects we have contact with ~150 general practitioners and we have established a collaboration with the low-threshold service UngArena.

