The combination of elaborate marketing campaigns in social media and the research app will allow for a very efficient recruitment, eligibility check and data collection. Those being interested will register online after confirming inclusion criteria: 1) between the ages of 16-19, 2) have previously sought professional help for anxiety and/or depressive symptoms, 3) have been feeling fine or mostly fine for the last two months. Before further assessment and trial inclusion, the adolescent will sign informed consent digitally. After consent is obtained, they will be invited to download the research app. To ensure eligibility, preassessment with the digitalized self-report format of the clinical interview Composite International Diagnostic Interview 5th revision (CIDI 5.0 (31)) will be conducted to make sure that the adolescent have had a previous episode of depression and/or an anxiety fulfilling the DSM-5 criteria, and no current ongoing episode or ongoing anxiety disorder before trial entry and randomization are conducted.

Table 1. Participant eligibility

Inclusion criteria

 • Currently in full or partial remission for a minimum of 2 months from a depressive disorder or an anxiety disorder. • Age between 16-19. • Native or fluent Norwegian or Scandinavian language skills. • Willingness to take part even when allocated to the non-preferred intervention.
Exclusion criteria

 • Ongoing depressive disorder, ongoing anxiety disorder. • Recent (within ~1 year) completion of the “Tankevirus”-intervention. • No available smartphone.

PRIMARY ENDPOINT: The primary endpoint will be time until relapse and number of relapses to depression during the 12-months follow-up post-randomization. To assess relapse, the app will give notifications for biweekly assessments with the ultra-brief PHQ-4 (32) assessing both anxiety and depressive symptoms. If the depression subscale indicates relapse (score ≥ 3), the remaining questions from PHQ-A (33), that is the adolescent version of PHQ-9 (34), will pop-up. The items in PHQ-9 aligns with the diagnostic criteria for major depressive disorder as described in the Diagnostic and

Statistical Manual of Mental Disorders (35) and an algorithm can therefore indicate depressive relapse (36). This procedure of biweekly assessments will also provide a precise measure of time to relapse.

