STATISTICAL POWER: For the primary endpoint investigating number of relapses within the follow-up period, we will conduct a fixed effects omnibus ANOVA. Presuming Cohen's $f = .25$, alpha = .0167 (.05/3; Bonferroni corrected) and power = .8 including three groups, we will require a total sample size of 207 (GPower 3.1). Presuming 15 % dropout, we will need 238 adolescents to take part in the study. For time to relapse, the power analysis was performed using Monte Carlo simulation. A large pool of simulated survival data was generated, reflecting a hazard ratio of 0.6 between two groups, a 15% annual dropout rate with competing risk, and a 1-year observation period. The simulation titrated the sample size, drawing 10.000 random samples at each step and fitting Cox proportional hazards models. Power was estimated as the proportion of samples yielding statistically significant results at the 0.05 level. The analysis concluded that approximately 165 individuals per group, meaning that a total of 495 adolescents would be required to achieve 80% power for detecting a hazard ratio of 0.6 under the specified conditions. This simulation method accounts for the complexities of survival data, including censoring and limited observation time, providing a robust sample size estimate for the study design. All randomized participants will be subjected to analysis in accordance with an intention to-treat approach. The multiarmed parallel group randomized trial will be reported according to the extensions recommended by CONSORT (44).

RISK: Recruitment is the main risk factors of this trial. A few trials are currently under way in adolescent populations (e.g., StayFine trial (16), RuMeChange (15)) and in the first, they were in contact with 3018 adolescent during a three-year period. Their strict inclusion criteria and elaborate pre-inclusion assessments hindered several from participating, but still they had 589 eligible

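### A fixed-effects ANOVA is a poor choice for the number of relapses: if pairwise contrasts use its pooled error, app versus control looks too precise and guided versus app not precise enough

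*Protocol*

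**What the plan says.** Protocol section 1.3, under PRIMARY ENDPOINT: "The primary endpoint will be time until relapse and number of relapses to depression during the 12-months follow-up post-randomization". The count is therefore primary alongside time to relapse.

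Under STATISTICAL POWER in the same section: "For the primary endpoint investigating number of relapses within the follow-up period, we will conduct a fixed effects omnibus ANOVA". Although the sentence sits in the sample-size paragraph, it commits to an analysis. The sizing uses Cohen's f = .25, with "alpha = .0167 (.05/3; Bonferroni corrected) and power = .8 including three groups", and arrives at this: "we will require a total sample size of 207 (GPower 3.1"). Enrolment is set by the other half of the endpoint: "approximately 165 individuals per group, meaning that a total of 495 adolescents would be required".

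Under HYPOTHESIS the guided arm is expected to be "more effective in reducing number of relapses and time to relapse during the follow-up period when compared to the app-based approach", and the app in turn to be better than assessment-only. The protocol names no count model, robust or unequal-variance method, or transformation for the number of relapses.

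**The concern.** A fixed-effects ANOVA estimates one error variance from all three arms. For a small count the variance grows with the mean, so arms with different relapse rates have different variances. The hypothesis says the rates will differ, so the equal-variance assumption breaks down in the very case in which the interventions work.

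The pooled variance is then an average over a high-variance control arm and lower-variance intervention arms. It is too small for app versus control and too large for guided versus app. The second contrast is the first half of the main hypothesis, and section 2.1 relies on it to settle how much clinician involvement is needed. An inflated error there makes it easier to miss a benefit of the therapist, while app versus control is tested somewhat too liberally.

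**Working it through.** **The plan's own figure.** For an omnibus F test with noncentrality N·f², f = 0.25, three groups and alpha = .0167, the smallest N divisible by 3 with at least 80% power is 207 (power 0.805). This agrees with the protocol. Cohen's f is defined with one common within-group standard deviation, so the sizing carries the same assumption as the analysis.

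**Inputs.** From the protocol:
- 165 per arm and 15% dropout, so 165 × 0.85 = 140 analysable per arm
- alpha .0167
- a ratio of 0.6, borrowed from the time-to-relapse planning ("reflecting a hazard ratio of 0.6 between two groups")

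Assumed, because the protocol gives no relapse rates:
- A control mean of 0.63 relapses per year. With a constant hazard and no overdispersion this means 1 − exp(−0.63) = 47% relapsing within 12 months.
- Variance = μ + kμ², with dispersion k = 0 (Poisson), 1 or 2. The 47% holds only at k = 0. At k = 1 the share with any relapse is 1 − 1/1.63 = 39%, and at k = 2 it is 1 − 1/√2.26 = 33%.

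**Error bars.** For arms i and j, true SE ÷ pooled SE = √[(v_i + v_j) / (2·v̄)], where v̄ is the mean of the three arm variances. Take a ratio of 0.6 at each step, giving means of 0.63, 0.378 and 0.227 for control, app and guided.
- k = 0: variances 0.630, 0.378, 0.227; v̄ = 1.235/3 = 0.412. Control–app √(1.008/0.823) = 1.11; control–guided √(0.857/0.823) = 1.02; app–guided √(0.605/0.823) = 0.86.
- k = 2: variances 1.424, 0.664, 0.330; v̄ = 2.418/3 = 0.806. The ratios are 1.14, 1.04 and 0.79.
- At most one relapse each: probabilities 0.467, 0.315, 0.203; variances p(1 − p) = 0.249, 0.216, 0.162; v̄ = 0.209. Control–app is 1.05 and app–guided 0.95.

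A value above 1 means the ANOVA error bar is too narrow, and below 1 too wide. Control versus guided is nearly right.

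**Simulated consequences** (140 per arm, alpha .0167, 20,000 trials per scenario):

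| Scenario (control mean 0.63) | Pooled ANOVA error | Robust log rate ratio |
|---|---|---|
| App = control, guided at ratio 0.6: app-versus-control type I error | 2.7–2.9% | near nominal |
| App = guided, both at ratio 0.6: guided-versus-app rejection | 0.6–0.8% | near nominal |
| Ratio 0.6 at each step: guided-versus-app power, k = 0/1/2 | 31/17/11% | 45/35/29% |
| 0.6 is the whole guided-versus-control effect (means 0.63/0.49/0.38): guided-versus-app power, k = 0/1/2 | 12/7/5% | 15/11/9% |

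If nobody relapses more than once, guided-versus-app power changes by about 0 to 5 points and app-versus-control type I error is about 2.0%.

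**Other assumed rates** (165 per arm, alpha .0167). With means 0.5/0.3/0.18, guided-versus-app power is 28% pooled versus 43% (k = 0) and 17% versus 34% (k = 1). With weaker effects, 0.5/0.4/0.32, it is 9% versus 12% and 6% versus 8–9%. When all three arms are equal, the omnibus test rejects in 1.5–1.6% of trials at nominal 1.67%, so its level holds.

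**The case against.** The strongest reply has four parts.

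- **The contrasts are inferred.** The protocol names only the omnibus test and the divided alpha. It does not say how pairwise contrasts are formed, and a statistical analysis plan, not available here, may do so with separate variances. This stands as a condition on the point. Still, pooled-error contrasts are what a fixed-effects ANOVA with .05/3 naturally implies.
- **The inflation is modest at the plan's alpha.** At two-sided 5% the same app-versus-control scenario gives about 7%, and a reader might infer that level of error for the trial. The documents do not support this: this endpoint is planned at .0167, where the figure is 2.7–2.9%. That is above nominal but small in absolute terms.
- **Counts may be close to 0 or 1.** Section 1.1 defines remission as at least two months without significant symptoms, so relapses cannot follow one another at once. This pushes towards the case with little distortion. It stands as a limit on size. On the other side, the protocol chose a count in addition to time to relapse, and two-weekly assessment over 12 months can record repeats.
- **The large power losses need a large effect.** Applying 0.6 twice makes guided versus control 0.36. The protocol states 0.6 only once, for two groups. With 0.6 as the whole effect, the loss is 3–4 points.

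In addition, the enrolment target of 495 rests on time to relapse and does not depend on this ANOVA.

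**Conclusion.** The point holds in direction. A pooled-variance ANOVA is ill suited to this count, and under the hypothesised ordering it misstates the precision of two of the three contrasts, provided those contrasts use the pooled error. Control versus guided, and the omnibus test when all arms are equal, are nearly unaffected.

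The size is uncertain because relapse rates and dispersion are not given. At alpha .0167 the loss of guided-versus-app power ranges from about 14–18 points (ratio 0.6 at each step) through 3–4 points (0.6 in total) to roughly 0–5 points (no repeat relapses).

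Two stronger conclusions are tempting. One is that the analysis is invalid and must be changed before the trial can proceed. The preserved omnibus level, the modest type I inflation and the separate time-to-relapse analysis do not support that. The other is that a count model would give guided versus app the power it needs. It would not: even after the change, power in these scenarios is 9–45%. This should be fixed as a low-cost improvement.

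**What to change.** Replace the ANOVA sentence with a negative binomial model of the relapse count by arm, or a Poisson model with robust standard errors. Report rate ratios with confidence intervals for the pairwise contrasts at the stated alpha. In the simulations under equal rates, the robust log-rate contrast rejected in 1.5–1.9% of trials at nominal 1.67%.

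The cost is a sentence in the protocol and the matching analysis code, with no extra participants or data. There are two small downsides. The effect is reported as a rate ratio instead of a mean difference, and the sample-size statement for this endpoint has to be restated on assumed relapse rates and dispersion in place of Cohen's f. That restatement should say openly what power guided versus app has at 495 enrolled. The change is best made before unblinding, so that it cannot appear data-driven.

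### The two parts of the primary endpoint are sized on alphas that do not fit together, and the 80% power belongs to one unnamed pair of arms

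*Protocol*

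**What the plan says.** All references are to the protocol. Section 1.3, PRIMARY ENDPOINT, defines one endpoint with two parts: "The primary endpoint will be time until relapse and number of relapses to depression during the 12-months follow-up post-randomization".

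Section 1.3, STATISTICAL POWER, sizes the parts separately:

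- **Number of relapses.** Here "we will conduct a fixed effects omnibus ANOVA", sized with Cohen's f of .25, power .8 and "alpha = .0167 (.05/3; Bonferroni corrected"). The result is 207, raised to 238 for dropout.
- **Time to relapse.** Survival data are simulated "reflecting a hazard ratio of 0.6 between two groups", with 15% annual dropout and one year of observation. On significance: "Power was estimated as the proportion of samples yielding statistically significant results at the 0.05 level". The result is "approximately 165 individuals per group, meaning that a total of 495 adolescents would be required to achieve 80% power". The RISK paragraph then uses 495 as the number to recruit.

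The aims are pairwise. The main hypothesis (section 1.3, HYPOTHESIS) has two steps. In the first, guided treatment "will be more effective in reducing number of relapses and time to relapse during the follow-up period when compared to the app-based approach". The second step sets the app against the control arm: "the app-based approach will be more efficacious compared to an assessment-only condition/care-as-usual". Section 1.2 and the DESIGN paragraph of section 1.3 compare both interventions with assessment only. Section 2.1 relies on the head-to-head comparison to settle how much clinician involvement is needed.

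**The concern.** A three-group omnibus F-test is one test. It needs no division by three on its own account, and the protocol does not say what the three stands for. If it stands for the three pairs of arms, the divisor belongs on pairwise tests. The only pairwise test in the paragraph is the Cox comparison, which carries none.

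Two things are at stake. First, the reader cannot tell which aim has 80% power, because the pair with hazard ratio 0.6 could be guided versus control, app versus control, or guided versus app. Second, the error rate for the primary endpoint as a whole cannot be read from the two printed alphas. If the scheme and the pair are still open when data arrive, the contrast described as the powered one can be chosen afterwards.

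**Working it through.** **1. Reproduce the ANOVA figure.** Inputs from the protocol: three groups, f = .25, power .8. Power comes from the noncentral F distribution with 2 and N − 3 degrees of freedom and noncentrality N·f². The smallest N in equal groups is:

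| alpha | N |
|---|---|
| 0.05 | 159 |
| 0.025 | 189 |
| .05/3 | 207 |

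At N = 207 the noncentrality is 207 × 0.0625 = 12.94 and power is 0.805. The protocol's 207 reproduces at .05/3 and not at 0.05, so the corrected alpha was really used.

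**2. Check the Cox figure.** The 165 per group cannot be reproduced outright, because no relapse risk is given. The event count behind 80% power can be found from Schoenfeld's formula with equal arms, d = 4(z_alpha + z_power)² / (ln HR)², where (ln 0.6)² = 0.2609:

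- Two-sided 0.05 (assumed): d = 4 × (1.960 + 0.842)² / 0.2609 = 120.3 events.
- One-sided 0.05 (the alternative): d = 4 × (1.645 + 0.842)² / 0.2609, about 95 events.

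With exponential relapse times and 15% annual dropout, 165 per group yields these counts if the one-year control risk is about 47% (two-sided) or about 37% (one-sided). So 165 is plausible at an uncorrected 0.05, but not confirmed.

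**3. Power of the same contrast at a corrected alpha.** Events are held at the number giving 80% at 0.05, and power is Φ(z_0.05 + 0.842 − z_alpha′), so it does not depend on the relapse risk:

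| alpha for the pair | two-sided | one-sided |
|---|---|---|
| 0.05 | 80% | 80% |
| .05/2 | Φ(2.802 − 2.241) = 71% | Φ(2.486 − 1.960) = 70% |
| .05/3 | Φ(2.802 − 2.394) = 66% | Φ(2.486 − 2.128) = 64% |

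A log-rank simulation of 10,000 trials (165 per arm, control risk 47%, two-sided) gave 79.6%, 70.5% and 64.6%.

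**4. Error rate across the two endpoint parts.** If success on either part supports a claim, and only one Cox contrast is tested, the upper bound is .0167 + .05 = .0667, or 6.7%.

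**5. Error rate across Cox pairs.** If each pair is claimed at two-sided 0.05 with no gate or order, simulated family-wise error when all three arms are equal is about 9% for the two hypothesised pairs and 12% for all three. With a global test at 0.05 before the pairwise tests it is 5.0%.

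**The case against.** The strongest reply is that neither alpha is shown to be wrong by itself. With three arms, a global test followed by pairwise tests at 0.05 holds the family-wise error, and so does a fixed sequence. The main hypothesis can also be read as a conjunction, guided better than app and app better than control. If both must succeed for the claim, each may be tested at 0.05 with no split. The .05/3 on the ANOVA is conservative and does not set the trial size: it leads to 238, against 495 from the Cox part. The full testing procedure may also stand in a statistical analysis plan that is not shown.

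Most of this stands, and it limits the point. A reader might infer that the trial has a family-wise error of 9% or 12%. The protocol does not support that, because it states no ungated scheme; those figures are conditional. A reader might also infer that the trial is too small. Bonferroni at .05/2 or .05/3 would take about 600 or 663 participants for 80% per contrast, but nothing in the protocol says that such a correction is intended for the Cox pairs.

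What does not fall away is the conflict on the page. A sequence, gate or conjunction would explain 0.05 on the Cox pair, but none of them explains .05/3 on one omnibus test beside it. Nor does any of them identify the pair with hazard ratio 0.6. These are statements in the protocol itself, not matters left to a later plan.

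**Conclusion.** The point holds as an inconsistency in the stated basis of the sample size. The 80% applies to one unidentified contrast at 0.05. It carries over to a contrast ranked first in a fixed sequence if that contrast is the hazard ratio 0.6 pair. It does not carry over to Bonferroni-corrected pairs, and it is not the chance that both hypothesised contrasts succeed.

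The loss from correcting is 9 to 14 percentage points two-sided, or 10 to 16 if the 0.05 was one-sided. It rests on hazard ratio 0.6 and on 165 per group really delivering 80% at 0.05. The 6.7% assumes that either endpoint part suffices. The protocol does not give the effects in the other two pairs, so no power is put on them here.

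It would go too far to conclude that 495 is wrong or that any effect estimate is biased. Neither follows from the protocol. The matter should be fixed before data are seen, and it does not call for a redesign.

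**What to change.** At unchanged sample size:

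1. Put both parts of the primary endpoint under one stated alpha scheme, saying whether either part suffices or both must succeed. Move, justify or drop the .05/3 on the omnibus test.
2. State the scheme for the Cox contrasts. The choice is the sponsor's: for example, a global two-degree-of-freedom test at 0.05 followed by pairwise tests at 0.05, or a fixed sequence with its order given.
3. Name the pair to which hazard ratio 0.6 refers, and state whether 0.05 is one- or two-sided.
4. Rerun the existing simulation with three arms. Report power for each hypothesised contrast under the chosen scheme, with the assumed relapse risk and the effect in each arm.

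The cost is protocol wording and one rerun, with no extra participants. The downside is that stated power for some contrasts will fall below 80%.

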1.3. Research questions and hypotheses, theoretical approach and methodology

RESEARCH QUESTION: Through a decentralized RCT investigating two digital interventions with differentiated levels of therapist-support, the goal is to expand knowledge about transdiagnostic relapse prevention strategies that can easily be scaled up and have the potential of cost-effectively reducing relapse rates for adolescents in an important phase of life. Alongside, collecting empirical

[figure not shown]
evidence for the association between repetitive negative thinking and relapse will increase knowledge regarding underlying mechanisms of relapse prevention strategies.

DESIGN: The trial is designed as a three-armed randomized single-blind open-label clinical trial (1:1:1) with stratification based on gender. It will not be possible to blind participants in the study due to the obvious differences between the interventions. We will investigate the effects of the “Tankevirus”-therapist-guided intervention and the “Tankevirus” smartphone app, respectively, and compare the effect of these transdiagnostic interventions to assessment only. All arms will be conducted in combination with care as usual. Assessments are done digitally, with no influence from the researcher. The primary endpoint of the trial will be analyzed blinded to treatment allocation. The trial will be preregistered with clinicaltrials.gov.

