Currently, there is no systematic relapse prevention strategies offered to this group within the health services. If the adolescent does receive care at any level within the health services, enrolment in this trial will not interrupt ongoing care regiments, nor will enrolment put any restrictions on initiating new care regiments, but we will ask them not to download other mental health apps during their participation. Ongoing care will be registered and will be controlled for when analysing the outcome.

GENDER: We will register the gender of the participants and conduct separate analysis to better understand the gender imbalance of experiencing depression. A low number of binary participants may hinder separate analysis for this group.

USER KNOWLEDGE: Adolescents 16-19 years of age have been involved in all stages of the development of the “Tankevirus”-interventions, from idea to product. Their voices have extensively influenced its current content, like its duration, scope, means of communication (i.e., short videos), examples, humour, illustrations, music, and ensuring that it meets their prior knowledge. The app received the highest-ranking score by DigiUng, the panel of youths advising The Norwegian Directorate of Health. For this project, we have initiated collaboration with the Competence Center for Lived Experience and Service Deployment (KBT), who specializes in bringing forward service user voices. By involving persons with lived experiences in our research group, we will ensure that this project cater their needs. Their voices have been heard in the development of this project, f. ex. regarding outcome measures, the participant burden, and their compensation, and will also be important when building recruitment campaigns, in designing and writing information material, and ensure that the workload associated with participation is manageable. They will also be important when interpreting and disseminating the results. In the planning phase, the project will also be discussed with the national youth user panel of FACT (Flexible Assertive Community Treatment).

2. Impact

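### Gender is to be studied by separate within-gender analyses, which give no direct estimate or test of a between-gender difference; one joint exploratory model, tied to the planned predictor analyses, would

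*Protocol*

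**What the plan says.** Three places in protocol section 1.3 bear on gender.

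- **GENDER paragraph.** "We will register the gender of the participants and conduct separate analysis to better understand the gender imbalance of experiencing depression". The next sentence reads "A low number of binary participants may hinder separate analysis for this group" (non-binary participants are presumably meant). It shows that an analysis within each gender group is intended. No between-gender contrast, joint model or interaction is named there.
- **Exploratory predictors** (just before SECONDARY OUTCOMES, and under ASSESSMENTS). The protocol plans exploratory work on what predicts relapse and what predicts benefit from each intervention, and lists gender among the baseline predictors of outcome. The GENDER paragraph does not refer to this.
- **DESIGN.** Randomisation is 1:1:1 "with stratification based on gender".

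The STATISTICAL POWER paragraph gives the figures used below: simulated data "reflecting a hazard ratio of 0.6 between two groups", power as the "proportion of samples yielding statistically significant results at the 0.05 level", the aim "to achieve 80% power for detecting a hazard ratio of 0.6", and, as the resulting size, "approximately 165 individuals per group, meaning that a total of 495 adolescents would be required".

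**The concern.** The stated purpose is to understand a difference between genders, but the named method looks at one gender at a time. A Cox model fitted in girls and another in boys each return an arm effect. Neither contains a gender term, so neither says by how much relapse differs between genders. Nor does either test whether the arm effect differs.

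What remains for the reader is to set two results side by side. The usual hazard is to take a significant result in one group and a non-significant one in the other as a difference. The trial is sized for all 165 participants per group, so every split by gender loses power, and the smaller group loses most. The protocol intends prediction results to inform staged care (section 2.1) and findings on predictors of treatment success to inform guidelines (section 2.2), so a gender-specific reading could have consequences.

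**Working it through.** **Inputs from the protocol (STATISTICAL POWER):** HR 0.6, alpha 0.05, 80% power, 165 per group, and "a 15% annual dropout rate with competing risk, and a 1-year observation period".

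**Assumptions, not in the protocol:** two-sided test; the event count implied by the stated power; equal relapse risk in both genders, so that the share of events equals the share of participants; and the gender mix, varied from 50:50 to 80% girls.

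**Step 1. The plan's own figure.** Schoenfeld events for one pairwise contrast: 4 × (1.960 + 0.842)² / (ln 0.6)² = 31.4 / 0.261 = 120.3, rounded up to 121. With 2 × 165 = 330 participants this needs a mean event probability of 121/330 = 36.7%. With exponential hazards and dropout hazard −ln 0.85 = 0.163, the expected event proportion in an arm with hazard h is h/(h + 0.163) × [1 − exp(−(h + 0.163))]. Setting 165 times the sum over hazards h and 0.6h equal to 121 gives h = 0.637, a control one-year relapse risk of about 47%. The protocol gives no control relapse rate, so 165 per group is attainable but cannot be confirmed.

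**Step 2. Power within each gender,** same HR 0.6 in both. With e events, power = Φ(√e / 2 × 0.511 − 1.96). For 80% girls:
- girls: e = 0.8 × 121 = 96.8, power = Φ(0.55) = 71%
- boys: e = 0.2 × 121 = 24.2, power = Φ(−0.70) = 24%

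**Step 3. Discordant verdicts.** The groups are disjoint, so the results are independent. P(girls only) = power in girls × (1 − power in boys) = 0.710 × 0.759 = 0.54. P(boys only) = 0.241 × 0.290 = 0.07. The sum is 0.61.

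**Step 4. Interaction test.** The SE of the difference in log HR is √(4/e₁ + 4/e₂). At 50:50 it is √(8/60.5) = 0.364, and power for a ratio of HRs of 0.6 is Φ(0.511/0.364 − 1.96) = 29%. At 80:20 the SE is 0.455 and the power 20%. With equal effects the test signals a difference in 5% of trials, its alpha.

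| Girls' share | Power girls / boys | Significant in girls only | Discordant either way | Interaction power, ratio of HRs 0.6 |
|---|---|---|---|---|
| 50% | 51% / 51% | 25% | 50% | 29% |
| 60% | 59% / 43% | 34% | 51% | 28% |
| 70% | 65% / 34% | 43% | 55% | 25% |
| 80% | 71% / 24% | 54% | 61% | 20% |

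The ratio of HRs detectable with 80% power is exp(−2.80 × SE): 0.36 at 50:50 and 0.28 at 80:20. If each separate test were run at 0.0167 with the same 121 events, girls-only results would occur in 23% to 48% of trials and discordant ones in 45% to 54%.

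**The case against.** A reader might infer that the protocol plans to claim efficacy in one gender and not the other, or that it is likely to reach a spurious conclusion of that kind. The documents do not support this. The GENDER paragraph speaks of who experiences depression. It mentions no comparison of arms by gender and no reading by p-values. The table therefore describes a use that the wording permits, not one that it states.

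Three further points stand.

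- It would be too strong to say that separate analyses cannot answer the question. Estimates from disjoint groups are independent, so the difference between two gender-specific arm effects can be formed with SE √(SE₁² + SE₂²), as in step 4. The problem is that this contrast is not planned in that paragraph.
- Between-gender questions are in substance open to the exploratory predictor analyses. Gender as a predictor of relapse is a main effect, and gender as a predictor of benefit is an interaction. The model form may properly sit in an SAP that is not shown, so its absence is not held against the protocol.
- The event count and gender mix are assumed. Equal relapse risk by gender sits uneasily with a paragraph that presupposes an imbalance. What drives the result is the share of events, so a higher relapse risk in girls would move the figures down the table.

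These points do not remove the mismatch. The one paragraph devoted to gender names a method, that method does not directly address its stated question, and nothing links it to the analyses that could. Stratifying randomisation by gender is sound and is no part of the criticism.

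**Conclusion.** The point holds as a correctable choice of method in an exploratory analysis. That within-gender analyses give no direct estimate or test of a between-gender difference needs no numerical assumption.

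The size is conditional. Suppose the separate analyses are applied to arm comparisons and judged by significance. With HR 0.6 in both genders, about 121 events per contrast and equal relapse risk, roughly 25% to 54% of trials would show significance in girls only, and 50% to 61% would show discordance in one direction or the other. An interaction test would signal a false difference in 5%. Of these inputs only the HR, the 0.05 level and the 80% power come from the protocol.

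The interaction test is itself weak, with about 20% to 29% power for a ratio of HRs of 0.6. It guards against false differences but would miss many real ones. The primary comparison and the sample size are not affected.

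**What to change.** In the GENDER paragraph, replace the separate analyses by one model on all participants, and state that it belongs to the exploratory predictor analyses in the same section. The text should specify:

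- a gender main effect for the difference in relapse, with 95% CI, taken from the model without the interaction or averaged over arms so that it does not refer to one arm only;
- an arm-by-gender interaction for the difference in treatment effect, with 95% CI;
- an exploratory label for both, with a note that the interaction has low power, so a non-significant result is not evidence of equal effects;
- gender-specific estimates with CIs as description only;
- that any statement of a gender difference rests on the main-effect or interaction estimate, never on comparing significance between groups.

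The cost is a change of wording. Gender is already recorded and used as a stratification factor, so no new data are needed. The change should be made before outcome data are seen.
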